7.1.3. Re-challenge Therapy

Participants may re-challenge therapy for any reason, including toxicity, according to prespecified criteria and with the explicit permission of the Medical Monitor.

If therapy has been stopped due to toxicity, the Investigator must confirm the toxicity is resolving (to at least Grade 2 or better severity) before attempting re-challenge.

If therapy has been discontinued for any other reason, that reason must be provided to the Medical Monitor.

7.2. Permanent Discontinuation/Withdrawal of a Participant from the Study

A participant may permanently discontinue/withdraw from the study at any time at their own request, or may be permanently discontinued/withdrawn at any time at the discretion of the Investigator for safety, behavioral, or compliance reasons. Any such participant will be permanently discontinued from the study interventions and the overall study at that time. If a participant withdraws consent for disclosure of future information, the Sponsor may retain and continue to use any data collected before such a withdrawal of consent, subject to any limitations under applicable data privacy and data protection laws.

If a participant permanently discontinues/withdraws from the study, that participant may request destruction of any samples taken and not tested, and the Investigator must document this in the site study records and notify the Sponsor.

If a participant permanently discontinues/withdraws from the study during the Treatment Phase, if possible, an ED Visit should be conducted, as shown in the SoA ([Table 1](#)). Refer to the SoA for details of the data to be collected at the time of study discontinuation and follow-up, and for any further evaluations that need to be completed.

If a participant permanently discontinues/withdraws from the study during the Post-Treatment Follow-up Phase prior to death, that participant will be censored from the OS analysis.

7.2.1. Criteria for Permanent Participant Discontinuation/Withdrawal from the Study

All participants should be encouraged to complete all study evaluations. However, participants may withdraw consent to participate in this study at any time without penalty or loss of benefits to which they are otherwise entitled.

Every reasonable effort should be made to determine the reason a participant withdraws consent to participate in this study; this information should be recorded on the appropriate page(s) of the eCRF. Where participants discontinue study intervention prematurely without withdrawing consent, reasonable efforts should be made to obtain all protocol-specified assessments to avoid losing outcome data needed to evaluate safety.

Participants may withdraw from the study at their own discretion (or at the discretion of the Investigator) for any reason at any time. The list of reasons for withdrawing participants from the study may include, but is not limited to, the following:

- Occurrence of an AE that, in the opinion of the Investigator, warrants the participant's permanent withdrawal from treatment.
 - In the event of IMP (lerociclib) withdrawal due to the occurrence of a nonserious AE, the study site should notify the Sponsor or Sponsor's representative as soon as possible.

- In the event of study intervention withdrawal due to the occurrence of an SAE, the Medical Monitor or representative must be notified within 24 hours.
- Participants withdrawn secondary to an ongoing, nonserious AE, regardless of causality, or an SAE that is not related to IMP (lerociclib) must be followed clinically until 14 days after the last dose of IMP was administered.
- Participants withdrawn secondary to an ongoing SAE that is considered related to IMP (lerociclib) must be followed clinically until resolution or stabilization.
- Significant noncompliance, defined as refusal or inability to adhere to the prescribed dosing and follow-up regimen

Note: As described previously, for any participant whose compliance with any study intervention falls below 80%, potential discontinuation from study treatment is to be discussed between the Investigator and Sponsor before a final decision is made.

- Request of the participant, Investigator, or study Sponsor
- Withdrawal of informed consent
- Lost to follow-up (must have at least 2 documented attempts to contact the participant)
- Death

All data and lab samples collected prior to the date of withdrawal of consent will remain in the clinical database and at the laboratory vendor.

7.2.2. Replacement of Study Participants

Participants who do not ever receive the IMP (lerociclib) will be replaced. Any replacement participant will receive a new participant number.

7.3. Lost to Follow-Up

A participant will be considered lost to follow-up if that participant repeatedly fails to return for scheduled visits and is unable to be contacted by the study site.

The following actions must be taken if a participant fails to return to the clinic for a required study visit:

- The site must attempt to contact the participant and reschedule the missed visit as soon as possible (and within the visit window, where one is defined), counsel the participant on the importance of maintaining the assigned visit schedule, and ascertain whether the participant wishes to and/or should continue in the study.
- In cases in which the participant is deemed lost to follow-up, the Investigator or designee must make every effort to regain contact with the participant (where possible, 3 telephone calls and, if necessary, a certified letter to the participant's last known mailing address or local equivalent methods) and regain any remaining IMP from the participant. The Investigator should be making every effort to collect any unused medication. These contact attempts should be documented in the participant's medical record/eCRF.

- Should the participant continue to be unreachable, that participant will be considered to have withdrawn from the study.
- Site personnel, or an independent third party, will attempt to collect the vital status of the participant within legal and ethical boundaries for all participants enrolled. Public sources may be searched for vital status information. If vital status is determined as deceased, this will be documented and the participant will not be considered lost to follow-up. Sponsor personnel will not be involved in any attempts to collect vital status information.

A participant will be considered lost to follow-up after 3 months of documented contact attempts.

7.4. Criteria for Potential Stoppage (Permanent Discontinuation) of the Study

The Sponsor will review the evaluable data, including any emerging safety signals attributed to study drug, and will consider whether the permanent stoppage (discontinuation) of the study may potentially be appropriate. Additional details will be provided in the DSMB Charter document, as described in Section [10.1.5.1](#).

As noted in Section [4.4](#), stoppage (permanent discontinuation) of the study may also occur in any of the following circumstances:

- Overall, country-/region-specific, or site-specific stoppage by the Sponsor at any time, for any reason
- Stoppage in a specific country or region by the relevant Health Authority
- Stoppage at a specific site by the relevant IRB/IEC or by the Principal Investigator (refer to the relevant portion of the appendix on governance [[Section 10.1.9.3](#)])

8. STUDY ASSESSMENTS AND PROCEDURES

Study procedures and their timing are summarized in the SoA ([Table 1](#)). Protocol waivers or exemptions are not allowed.

Immediate safety concerns should be discussed with the Sponsor immediately upon occurrence or awareness to determine if the participant should continue or discontinue study intervention.

Adherence to the study design requirements, including those specified in the SoA, is essential and required for study conduct.

All Screening evaluations must be completed and reviewed to confirm that potential participants meet all eligibility criteria. The Investigator will maintain a Screening log to record details of all participants screened and to confirm eligibility or record reasons for Screening failure, as applicable.

Procedures conducted as part of the participant's routine clinical management (eg, blood count) and obtained before signing of the ICF may be used for Screening or baseline purposes provided the procedures met the protocol-specified criteria and were performed within the timeframe defined in the SoA.

The maximum amount of blood collected from each participant over the duration of the study, including any extra assessments that may be required, will not exceed approximately 300 mL.

Repeat or unscheduled samples may be taken for safety reasons or for technical issues with the samples.

Participant Identification Card

On Day 1 of Cycle 1, all participants will be given a participant identification card identifying them as participants in a research study. The card will contain study site contact information (including direct telephone numbers) to be used in the event of an emergency. The Investigator or qualified designee will provide the participant with a participant identification card immediately after the participant provides written informed consent.

Medical History

A medical history will be obtained by the Investigator or qualified designee. The medical history will collect all medical and surgical conditions that the Investigator considers to be clinically significant and relevant. Details regarding the disease for which the participant has enrolled in this study will be recorded separately and not listed as medical history.

Calibration of Equipment

The Investigator (or qualified designee) is responsible for ensuring that any device or instrument used for a clinical evaluation/test during the study that provides information about eligibility criteria and/or safety or efficacy parameters is suitably calibrated and/or maintained to ensure that the data obtained are reliable and/or reproducible. Equipment calibration documentation is to be retained at the study site and available for inspection.

8.1. Efficacy Assessments

Planned timepoints for all efficacy assessments are provided in the SoA ([Table 1](#)).

8.1.1. Antitumor Activity Assessments

For tumor assessment, all sites of disease, including but not limited to the chest, abdomen, and pelvis, should be assessed radiologically by CT or MRI at Screening and every 8 weeks for the first 12 months, then every 12 weeks until the occurrence of disease progression ([Table 1](#)). A central imaging vendor will be used to collect and hold these images for possible future review by independent radiologists. Objective response data collected for the clinical study report will be based on Investigator assessment.

Scans (CT or MRI) obtained prior to informed consent will not need to be repeated if performed within 28 days prior to dosing. Radionuclide bone scans shall be performed at Screening for all participants and annually thereafter or as clinically indicated. All participants with a CR must have a radionuclide bone scan as part of confirmation of the CR. Additional scans may be obtained at the discretion of the Investigator, if clinically indicated.

Participants with bone-only disease will be followed with bone scans only at Screening and every 12 weeks on treatment.

If a participant shows a radiological response (CR or PR), a confirmatory radiological assessment will be performed at least 4 weeks after the response was first noted. Participants who have a confirmed CR will have a bone scan to confirm absence of bony metastases.

For all participants (1L or 2L populations), if they remain on therapy for 12 months following enrollment, the timing of CT or MRI scans should be lengthened to every 12 weeks.

The same method of assessment (CT or MRI) should be used to characterize tumors at Screening and at all follow-up assessments. If PET is used, it should also be accompanied by spiral CT or MRI.

Investigators should follow RECIST v1.1 Guidelines ([Eisenhauer 2009](#)) for tumor assessments and determination of overall response.

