- f. Predose and postdose blood samples for lerociclib concentration measurement are to be collected prior to and following the dose of lerociclib on Day 1 and Day 15 of Cycle 1, and on Day 1 of Cycles 2, 3, 4, and 5. The postdose blood sample can be collected between 2 hours and 6 hours (\pm 10 minutes) after the administration of lerociclib. It is important to record the actual time of collection. If the participant is due for a 2- or 6-hour 12-lead ECG assessment, the PK sample may be drawn at the same timepoint but should be obtained after the ECG.
- g. Radionuclide bone scans shall be performed at Screening for all participants every 8 weeks (\pm 7 days) for the first 12 months and every 12 weeks thereafter if initial bone scan is positive for bony lesion. If initial bone scan is negative for bony lesion, bone scan should be done annually or as clinically indicated per Investigator standard of care. All participants with a CR must have a radionuclide bone scan as part of confirmation of the CR. Additional bone scans may be obtained at the discretion of the Investigator, if clinically indicated. Participants with bone-only disease may be followed only with bone scans at the discretion of the Investigator. If CT or bone scan have been done for regular clinical care within 28 days before receiving the first dose of lerociclib, these may be used as baseline scans.
- h. Subsequent cycles may be postponed up to 14 days due to lerociclib interruption. Note that subsequent cycles should start on the original schedule (ie first dosing date).
- i. Participants in the 1L and 2L populations will receive the Investigator's choice of letrozole 2.5 mg daily or fulvestrant 500 mg (dosed according to schedule specified in the protocol).

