- j. All premenopausal or perimenopausal female participants, and all male participants, must be receiving goserelin for at least 28 days prior to entering the study and will remain on goserelin throughout the study, in accordance with the prescribing information and according to the study site's standard practice. The goserelin dosing schedule is decoupled from the rest of the study visit schedule, with each participant's "goserelin CID1" determined as the date of their most recent goserelin dose before entering the study + 28 days. Goserelin dosing will continue on a q28d basis throughout the participant's time on study. All of the participant's non-goserelin-dosing study activities are to occur as shown in the Schedule of Activities.
- k. After the Safety Follow-up Visit, survival follow-up should be attempted every 12 weeks for each participant in the long-term Survival Follow-up Phase. Follow-up can be performed via telephone, clinic visits, or by receiving information from a family member or another provider who is administering care. Any anticancer therapies used will be recorded where possible, as well as any changes to participant pregnancy status (as applicable).
- l. CT or MRI scans obtained prior to informed consent will not need to be repeated if performed within 28 days prior to dosing with lerociclib.

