4. STUDY DESIGN

4.1. Overall Design

This is a multicenter, single-arm, open-label study to evaluate the safety and efficacy of lerociclib administered in combination with standard endocrine therapy in female or male participants with HR+/HER2- mBC.

The study population will consist of newly diagnosed, treatment-naïve participants with HR+/HER2- mBC (collectively referred to as the first-line, or 1L, population) and participants with HR+/HER2- mBC who have already progressed on first-line endocrine therapy such as tamoxifen, anastrozole, or letrozole (collectively referred to as the second-line, or 2L, population).

Approximately 100 participants will be enrolled and dosed in the study, with approximately 50 participants enrolled and dosed for each line of therapy (1L or 2L). All premenopausal or perimenopausal female participants, and all male participants, must be receiving goserelin for at least 28 days prior to entering the study and will remain on goserelin throughout the study, in accordance with the prescribing information and according to the study site's standard practice. The schedule for administration of goserelin for each individual participant is decoupled from the rest of the study visit schedule, and will be determined by the date of the participant's most recent dose of goserelin at the time of study entry (with "goserelin C1D1" defined as the date of the participant's most recent dose + 28 days, then every 28 days subsequently).

All study participants (1L and 2L populations) will receive the Investigator's choice of AI (letrozole) or fulvestrant plus lerociclib 150 mg BID. All participants should be treated according to the best current practice guidelines and standard of care within each institution or country where the study is conducted.

The study will consist of 3 phases: a Screening Phase of up to 42 days in duration; a Treatment Phase (which includes a Safety Follow-up Visit occurring 30 days after the last dose of lerociclib); and a Post-Treatment Follow-up Phase (which includes a Survival Follow-up Phase) that will continue until death, loss of follow-up, withdrawal of consent, or the end of the study (whichever occurs first).

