4.2.1 Definitions

‘Baseline’ is defined as the last available pre-treatment assessment, where treatment includes the investigational medicinal product (IMP) or any non-investigational medicinal product (NIMP).

‘End of Treatment’ is defined as the value obtained at the EOT visit. If a value for a given parameter was not collected at the EOT visit the last available value collected prior to the EOT visit may be used.

‘End of Study’ (EOS) is defined as the last available post-treatment assessment.

‘Study Day’ will be calculated relative to the date of first exposure to lerociclib. For assessments prior to first exposure, Study Day = Assessment Date – Date of First Exposure. For assessments on or after first exposure date, Study Day = Assessment Date – Date of First Exposure + 1.

The timing of events may also be presented as the Cycle Number and Day (or CXDY), where X is the cycle number and Y is the number of days since the first day of lerociclib treatment in the cycle + 1.

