4.10.1.3 Visit Windows

Analysis visit windows will be created based on the schedule of assessments in the protocol (Appendix 6.1) as shown below. Any visits outside the visit window will be considered “Unscheduled” and not summarized at a scheduled visit. If multiple records are mapped to the same visit, the one closest to the date of the scheduled assessment will be used. If there is an equal distance from the date of the scheduled assessment, the latest record will be used.

| Visit | Study Day Window |
|------------------|--|
| Screening | [-42, -1] |
| Cycle 1 Day 1 | 1 |
| Cycle 1 Day 15 | [13, 17] |
| Cycle 2 Day 1 | [27, 31] |
| ... | [expected day – 2 days, expected day + 2 days] |
| EOT/ED | [last dose day, last dose + 15 days] |
| Safety Follow-up | [last dose + 25 days, last dose + 35 days] |

For tumor evaluations, the following windows will be implemented:

| Visit | Study Day Window |
|---|--|
| Screening | [-42, -1] |
| Cycle 3 Day 1 | [50, 64] |
| Every 2 cycles (8 weeks) during first 12 months and every 3 cycles thereafter (12 weeks) until EOT/ED | [expected day – 7 days, expected day + 7 days] |
| EOT/ED | [last dose day, last dose + 15 days] |

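### Baseline study scans may be 42 days old at first dose but reused scans only 28; the excess of up to 14 days can bias ORR and PFS against lerociclib

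*Protocol*

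**What the plan says.** Protocol 4.1 provides for "a Screening Phase of up to 42 days in duration". The Screening column of the SoA (Protocol 1.3, Table 1), which holds the baseline tumour evaluation, runs from Day -42 to Day -1. SAP 4.10.1.3 gives imaging its own table, introduced by "For tumor evaluations, the following windows will be implemented", and its Screening row accepts the same range. Under SAP 4.2.1, Study Day "will be calculated relative to the date of first exposure to lerociclib", so Day -42 means 42 days before the first dose.

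Reused scans have a tighter limit. Protocol 8.1.1 says: "Scans (CT or MRI) obtained prior to informed consent will not need to be repeated if performed within 28 days prior to dosing". SoA footnote l says the same. Footnote g says of CT and bone scans done in regular care: "within 28 days before receiving the first dose of lerociclib, these may be used as baseline scans". Protocol section 8 lets routine procedures from before consent serve as baseline "provided the procedures met the protocol-specified criteria and were performed within the timeframe defined in the SoA", which adds no separate limit on scan age.

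No footnote caps the age of a tumour scan taken after consent. SAP 4.2.1 takes baseline as the latest assessment before treatment, with no age limit.

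**The concern.** A pre-consent scan from Day -30 falls outside the reuse allowance, while a study scan from Day -42 stands as baseline. The age of a scan matters equally for both, and the documents give no reason for the difference.

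The stake is the efficacy estimates. Protocol 8.1.1.2 defines PR as a 30% fall from the baseline sum. It defines PD as a 20% rise, with at least 5 mm absolute, over the smallest sum on study, which may be the baseline. A new lesion is also PD. PFS starts at first lerociclib (SAP 4.10.3.2). If tumours grow between scan and first dose, PR becomes harder to reach, part of the PD margin is used up before any drug is given, and a lesion that appeared before dosing counts as progression on treatment. The study has one arm, so no comparator shares the bias.

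**Working it through.** **Inputs from the documents.** Maximum age of a study scan: 42 days (SoA Screening column; SAP 4.10.1.3). Maximum age of a reused scan: 28 days (Protocol 8.1.1; SoA footnotes g and l). Excess: 42 - 28 = 14 days. PR and PD thresholds: 30% and 20% (Protocol 8.1.1.2).

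**The plan's own precision figure.** 0.80 × 50 = 40 participants with measurable disease per line. The largest 95% half-width for ORR is 1.96 × √(0.25/40) = 15.5 points by the normal approximation. The exact Clopper-Pearson interval at 20/40 is 33.8% to 66.2%, a half-width of 16.2 points. Both agree with the stated figure of about 16% (Protocol 9.4; SAP 4.12). The present point does not depend on it, but it gives a scale.

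**Assumption.** The documents give no growth rate. I assume volume doubling times (DT) of 60, 100, 180 and 365 days, with diameter growing as the cube root of volume.

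**Formulas.** For a scan d days before first dose:
- growth factor g = 2^(d / (3 × DT))
- shrinkage from the size at first dose needed for PR = 1 - 0.70/g
- growth after first dose that reaches the 20% PD threshold = 1.20/g - 1 (the 5 mm rule must also be met)

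Example, DT = 60 and d = 42: g = 2^(42/180) = 1.176. PR needs 1 - 0.70/1.176 = 40.5%. PD is reached at 1.20/1.176 - 1, about 2.1%.

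| DT (days) | Growth before dose, 42 d / 28 d | Shrinkage needed for PR, 42 d / 28 d | Growth to PD threshold, 42 d / 28 d |
|---|---|---|---|
| 60 | 17.6% / 11.4% | 40.5% / 37.2% | 2.1% / 7.7% |
| 100 | 10.2% / 6.7% | 36.5% / 34.4% | 8.9% / 12.5% |
| 180 | 5.5% / 3.7% | 33.7% / 32.5% | 13.7% / 15.8% |
| 365 | 2.7% / 1.8% | 31.8% / 31.2% | 16.9% / 17.9% |

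The extra 14 days therefore raise the shrinkage needed for PR by 3.3, 2.1, 1.2 and 0.6 points.

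**Effect on ORR, worst case.** Assume that every scan is at its age limit, that true ORR against a scan on the day of dosing is 40%, and that best change is log-normal with log-SD s of 0.3 to 0.5. Observed ORR = Φ(z − ln g / s), where Φ(z) = 0.40.

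| DT (days) | All scans 42 days old | All scans 28 days old |
|---|---|---|
| 60 | 21.4% to 28.2% | 27.0% to 32.0% |
| 90 | 27.0% to 32.0% | 31.1% to 34.6% |
| 365 | 36.6% to 38.0% | 37.7% to 38.6% |

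At DT = 90 the 14 days account for 31.1 - 27.0 = 4.1 points (s = 0.3) or 34.6 - 32.0 = 2.6 points (s = 0.5).

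**The case against.** The best counter-argument concerns size. A reader might infer that six weeks of growth are wrongly admitted, and compare a 42-day-old scan with one taken on the day of dosing. The documents do not support that comparison, because their own standard for reused scans already tolerates 28 days. Only 14 days are at issue, and most of the pre-dose growth in the table would remain under a 28-day limit. At slow growth the difference is trivial: 31.8% against 31.2% at DT = 365. Slow growth is also plausible, since the protocol excludes symptomatic visceral disease and assumes a median PFS of 24 months. All of this stands.

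A reader might also infer that 1L participants are untreated during screening, that 2L participants have only just progressed, or that 2L tumours grow faster, so that the bias differs by line. None of this is in the documents. Inclusion criterion 4 requires documented progression for 2L but sets no recency limit, no washout of earlier endocrine therapy is specified, and participants on goserelin have had it for at least 28 days before entry.

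The consequence is limited. The primary endpoint is adverse event incidence, nothing is formally tested, and the bias runs against the drug, so it cannot inflate an efficacy claim. Protocol 8.1.1 also sends investigators to RECIST v1.1, but neither document quotes a limit on baseline scan age from it, and none is relied on here.

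What survives is the unexplained difference between two kinds of baseline scan, and a bias of known direction whenever tumours grow before dosing.

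**Conclusion.** The point holds. Study scans may be up to 14 days older at first dose than the protocol allows for reused scans. Provided tumours grow in that interval, ORR is biased downward and progression is called too readily. CBR, DOR and TTR are affected less.

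The size is modest and uncertain. Across assumed doubling times of 60 to 365 days, the excess costs 3.3 to 0.6 points of required shrinkage for PR. It also lowers the post-dose growth that reaches the PD threshold from 7.7% to 2.1% at the fast end and from 17.9% to 16.9% at the slow end. These are worst cases for a participant scanned on the earliest permitted day. The documents give neither growth rates nor a distribution of scan ages, so the effect on the reported estimates cannot be known in advance. The affected results are secondary and descriptive, with an ORR half-width of about 16 points per line.

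**What to change.** **Participants not yet dosed.** In the SoA and Protocol 8.1.1, state that all baseline tumour imaging (CT, MRI and bone scan), before or after consent, must fall within 28 days before the first dose of lerociclib. This extends a limit the protocol already uses.

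**Participants already dosed.** Keep their scan as baseline. Do not simply narrow the SAP tumour window to Day -28. If the baseline definition in SAP 4.2.1 governs, that edit changes nothing. If the window governs, scans from Day -42 to Day -29 become unscheduled, and those participants could fall under the row of SAP Table 2 that censors PFS at first exposure when there is no baseline assessment. Their measurable-disease status for the Response Evaluable set could also be put in doubt. Instead, add to the SAP a listing of days from baseline scan to first dose, and a sensitivity analysis that repeats ORR and PFS without participants whose scan was older than 28 days, with the number excluded by line.

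**Cost.** A short edit to the SoA and 8.1.1, plus one listing and one repeat analysis from dates already needed. The downside is an occasional repeat scan when screening overruns, as already applies to pre-consent scans. If few scans exceed 28 days, the listing will show it and settle the matter.
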